In a pilot-study completed by our research-partners at the Wilson-Centre in Toronto, Canada, they compared groups of *discovery followed by direct discovery* (DD) with *instruction followed by discovery* (IP). In the case of DD, the participants, where given the materials needed to complete a simple suture, and a finished suture to look at. After the discovery-phase, they were parred with an instructor who demonstrated how it was to be performed. In the IP-case they were first instructed on how to perform the suture, and were afterwards allowed to practice it. At the end of the course both groups were given a post-test of ability, and a week-later both groups were given a retention test as well as a transfer test. The pilot-study included 26 participants in total, divided in two groups of 13. The participants were randomized, and everything was filmed and scored by blinded raters after an international standard. There were no significant results for the immediate post-test as well as the retention test. But in the case of the transfer test, the DD-group was far superior.

Our study will expand on the pilot-study to provide a comparison of guided discovery to traditional instruction for the learning of suturing tasks in surgery, seeing if Guided-discovery-learning works in a much larger research group. Using a double randomized, mixed-methods experimental design, we will investigate the effect of discovery followed by direct instruction (DD) vs. instruction followed by practice (IP) for the acquisition and two types of transfer of surgical skills. To understand *how* and *why* guided-discovery learning changes the learning processes of trainees, we will also film and analyze the interactions of a small-subset of participants in each condition as well as conducting focus-group interviews. Using an exploratory approach, we will explore how discovery learning prior to direct instruction might

change participants' interactions with instructors and task compared to their interactions during initial direct instruction. We will seek to uncover which exploratory approach or approaches provide the best qualitative data. This part is elaborated and investigated in a separate additional protocol.

We hypothesize that:

- 1) Participants in the DD condition will be better able to transfer their knowledge to learning a new skill (i.e., preparation for future learning).

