- 2) Participants in the DD condition will have equivalent performance to IP on post-test, but a similar or slightly improved performance on transfer of suturing skill to a more complex task (near-transfer).
- 3) Participants in the DD condition will interact differently with instructors and will use their learnings from the discovery phase to scaffold their learning during the direct instruction phase as well as interacting differently with the task at hand.

PERSPECTIVES

Faculty instructors are a limited resource in formal simulation-based training during post-graduate training. The rise of structured learning activities such as surgical boot camps and the emphasis on greater feedback and support for trainees means that instructor time is at a greater premium than ever before. Instructors must take time away from their busy clinical and workplace-based education activities in order to teach. Not only does this cost the healthcare system, the time commitment can reduce willingness to participate in education. Additional costs may be incurred by programs that must offer financial incentives for instructors. This trade-off between education and clinical work occurs in all academic postgraduate programs. Given the cost and investment required to recruit faculty for training, research is needed to maximize the efficiency of faculty involvement¹³. Our work directly contributes to this goal by identifying how instructor guidance is most helpful to trainees. Guided-discovery may be one approach to reducing the cost of training and instructor time in both post-graduate as well as pre-graduate learning courses¹⁸.

Post-graduate training also requires that trainees develop autonomy and are able to learn new skills or concepts effectively (Scholar role; Competency 1, Enabling 1.1, 1.2)^{19,20}. Further, Medical Expert^{19,20} (Competency 3, Enabling 3.1, 3.4) stresses trainees' abilities to transfer their training when faced with uncertainty and or complexity in future scenarios. Guided-discovery may be an effective organizing principle for educational design that can achieve these competencies across a wide range of disciplines and training environments. Our proposal would thus establish evidence of efficacy for guided-discovery for these competency roles.

4. Objective and Outcome Measure

Objective	Outcome measure

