Primary outcome: To examine the effect of Guided-discovery-learning on far transfer of simple surgical skills	Difference in the two groups OSATS-scores on a far-transfer test evaluated by blinded raters
Secondary outcome: To examine the effect of Guided-discovery-learning on near-transfer of simple surgical skills To examine the primary learning-efficiency of the two types of teaching. To examine the effects on the different types of transfer for the intervention and control groups.	Difference in the two groups OSATS-scores on a near-transfer test evaluated by blinded raters Difference in OSATS-scores between immediate post-test. Difference in OSATS-scores between near-transfer and far-transfer-tests.
Explorative outcomes: To examine the difference in interaction between students receiving Guided-discovery, and those that didn't. To examine the difference in student interaction and approach to the task.	Using whole-room angle video recordings to observe the student-teacher interactions. Using task-focused video recordings to observe student-task interaction.
To examine different explorative approaches for examining the mechanics behind Guided-discovery To examine how students experienced the training.	Using think aloud video-recordings for select students. Using focus group interviews

5. Study Design

The study is a randomized experimental study comparing guided-discovery-learning to traditional instructional learning. The study will be performed at CAMES, including n=64 pre-clinical students from the Medical Faculty of Copenhagen University. Part 1 of this study is an experimental design with two phases that will test the efficacy of guided discovery: Phase 1 will be a learning phase with the experimental manipulations, and Phase 2 will take place one week later and be outcome assessment for near- and far transfer. Part 2 of this study will be an observational analysis of films of a sub-set of participants in the DD and IP conditions in order to establish differences in learning behaviors

between both conditions and possible mechanisms for guided-discovery learning. The analysis will compare how participants interact with the task in each learning condition including documenting activities in each phase and interactions with instructors.

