For *Phase 1*, participants will be enrolled and randomly allocated to either the DD or IP groups. Each group consists of 8 participants. Participants will be randomized and the method of teaching allocated on the date of teaching. This will ensure generalization and ease of statistical analysis. In the DD group, participants will be given an example of a completed simple interrupted suture and their own skin pad, and suturing kit. They will then attempt to replicate the suture using the equipment and their own knowledge over 30 minutes. During the same period of time, the IP group will be taught using an instructor. The instructor will provide two demonstrations and explanations of the simple interrupted suture following which the participants will attempt the suture individually on their own skin pads and suturing kit (see Appendix A for Instructor directions; modifications will be made by an experienced surgical instructor on our team ST). The instructor will be told to provide feedback and guidance to the participants as well as answer any questions that participants may have. After the initial time, the DD group will be paired with an instructor who will provide two demonstrations and explanations of the suture and then interact with participants as they attempt the suture. The IP group will practice the suture without any further instructor guidance. At the end of the teaching session, all participants will complete a post-test requiring them to complete two simple interrupted sutures. Afterwards participants willing will be interview in short focus-group interviews. This entire session is expected to last 2 hours including consent and setup time.

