8.1 Description of Statistical Methods

To examine the effects of guided-discovery-learning contra traditional instructional learning, the following outcomes will be measured:

- Difference in OSATS scores between the control and intervention groups far-transfer-test
- Difference in OSATS scores between the control and intervention groups near-transfer-test
- Difference in OSATS scores between the groups post-test.
- Difference in OSATS scores between the groups development from post-test to transfer-test.

To establish whether there is a significant level of difference in the above-mentioned measurements, students t-test will be used. A statistical software package will be used to calculate these (SPSS vs. 25.0, Chicago, IL).

Analysis

Analysis of the experimental data will be through a mixed-effects linear models with participants as random and instructional condition as fixed factors. We will conduct separate analysis for each hypothesis. For hypothesis 1, we will analyze post-test and near-transfer test scores through a multivariate model (repeated MANOVA or similar depending on model fit and sampling adequacy)¹⁸ with the expectation of a significant interaction indicating differences between groups at near-transfer but not on post-test. To address hypothesis 2, we will analyze performance on the vertical mattress suture using a univariate model (ANOVA). Where appropriate, covariates for performance such as post-test performance will be included to account for individual skill difference and to increase statistical power. A mixed-effects model will also compare participants' near- and far-transfer test scores across both conditions.

The qualitative data analysis is described in more detail in the additional protocol

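### Section 8.1 lets the post-test score, an outcome measured after the randomised teaching, serve as a covariate for far transfer, with no rule for its use and no single primary test

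*Combined protocol and SAP*

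**What the plan says.** Section 4 names far-transfer OSATS, compared between the two arms, as the primary outcome. Section 5 identifies the far-transfer task as the vertical mattress suture, learned a week after the teaching.

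For analysis, section 8.1 offers several routes to the same comparison:

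- For all listed outcomes, "students t-test will be used".
- More generally, "Analysis of the experimental data will be through a mixed-effects linear models with participants as random and instructional condition as fixed factors".
- For the vertical mattress suture specifically, a univariate ANOVA, followed at once by the covariate sentence: "Where appropriate, covariates for performance such as post-test performance will be included to account for individual skill difference and to increase statistical power".
- Section 5 (Outcomes, Measures, and Data Collection) adds a repeated-measures analysis for the multiple attempts.

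None of these is designated primary.

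On the post-test, section 5 states: "At the end of the teaching session, all participants will complete a post-test requiring them to complete two simple interrupted sutures". Section 4 lists it as a secondary outcome: "Difference in OSATS-scores between immediate post-test". Section 8.1 also treats it as a response variable: "we will analyze post-test and near-transfer test scores through a multivariate model". The plan expects no difference on it. Section 3 hypothesises that "Participants in the DD condition will have equivalent performance to IP on post-test" and reports of the pilot that "There were no significant results for the immediate post-test as well as the retention test".

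**The concern.** A covariate that accounts for individual skill in a randomised comparison should be measured before the randomised treatment can affect it. The post-test comes after the teaching under comparison, so it mixes pre-existing ability with whatever DD or IP did to immediate performance. Conditioning on it no longer estimates the total effect of DD on far transfer, which is the section 4 primary outcome.

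The error can go either way. If DD leaves students somewhat worse immediately after teaching, adjustment pushes the far-transfer estimate towards DD. If DD leaves them better, adjustment removes part of a real effect.

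A second problem does not depend on any post-test difference. The covariate is to be used where appropriate, with no criterion, and the list of covariates is open. An unadjusted t-test and an optionally adjusted ANOVA both apply to the primary outcome, so the choice can be made after both results are known.

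**Working it through.** **Inputs from the documents.** Alpha 0.05, 80% power, 13 per group, raised to 16 for loss to follow-up (section 8.2). There are 64 participants, so 32 per arm at post-test and 16 per arm at far transfer. The pilot had 13 per group (section 3).

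**Assumptions, because the documents give no values.** Within-arm correlation r between post-test and far-transfer score of 0.3, 0.5 or 0.7; post-test difference (DD minus IP) from −0.5 to +0.5 SD; normal scores; independent participants; two-sided tests.

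**The plan's own figure.** The effect size in section 8.2 is incomplete in the available text, so the 13 per group cannot be reproduced directly. Solving backwards, a two-sided t-test with 13 per group has 80% power at 1.145 SD. At 16 per group the power for that effect is 88%.

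**Step 1: bias of the adjusted estimate.** Adjusted effect = total effect − b × (DD−IP post-test difference), where b is the pooled within-arm slope. In SD units b = r, so bias = −r × shift. For a shift of −0.5 SD:

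- r = 0.3: 0.3 × 0.5 = +0.15 SD
- r = 0.5: 0.5 × 0.5 = +0.25 SD
- r = 0.7: 0.7 × 0.5 = +0.35 SD

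**Step 2: rejection by the adjusted test when there is no true far-transfer effect.** Simulation, 16 per arm, 100,000 trials per scenario, ANCOVA with 29 df:

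| DD shift at post-test | r = 0.3 | r = 0.5 | r = 0.7 |
|---|---|---|---|
| 0 | 4.9% | 4.9% | 5.0% |
| −0.1 SD | 5.1% | 5.2% | 5.8% |
| −0.2 SD | 5.3% | 6.1% | 8.1% |
| −0.3 SD | 5.7% | 7.4% | 12.4% |
| −0.5 SD | 7.1% | 11.8% | 24.8% |

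The unadjusted t-test stays at about 5% throughout.

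**Step 3: the opposite direction.** With a true effect of 1.145 SD and DD 0.5 SD better at post-test, the adjusted estimate is 1.145 − 0.15 = 0.995, 1.145 − 0.25 = 0.895 or 1.145 − 0.35 = 0.795 SD. Power is 77%, 77% or 82%, against 88% unadjusted.

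**Step 4: free choice of test, no shift at all.** Counting a trial as positive if either the t-test or the ANCOVA is significant gives type I error of 6.4%, 7.3% and 8.4% for r = 0.3, 0.5 and 0.7.

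**Step 5: can equivalence at post-test be established?** The 95% CI half-width is t(0.975, 2n−2) × √(2/n):

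- Pilot, 13 per group: 2.064 × √(2/13) = 0.81 SD; power to detect a 0.5 SD difference, 23%
- This trial, 32 per arm: 1.999 × √(2/32) = 0.50 SD; power to detect a 0.5 SD difference, 50%

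No equivalence margin is stated. Neither sample can exclude differences of the size used in steps 2 and 3.

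**The case against.** The strongest reply is that the bias needs a post-test difference the plan does not expect. Under the hypothesised equivalence, adjustment is unbiased and raises power at 1.145 SD from 88% to 90%, 95% or 99%. For differences of 0.1–0.2 SD with r of 0.3–0.5, rejection is 5.1–6.1%, close to nominal; the largest figures need both a 0.5 SD deficit and a high correlation. This is correct, and the smaller values deserve as much attention as the larger. But equivalence is something the trial sets out to examine, and a non-significant result from 13 versus 13 does not establish it. The primary analysis should not depend on it.

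Second, the list of competing tests is longer than the real choice. With one score per participant the t-test and unadjusted ANOVA coincide, and with complete, balanced data on two sutures the mixed or repeated-measures test of condition reduces to the same comparison of participant means. That stands: the consequential choice is adjusted versus unadjusted. It is still open, and step 4 concerns exactly that pair.

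Third, the covariate sentence is general, and for near versus far transfer the post-test precedes the second allocation and is a legitimate baseline. That also stands; the concern is confined to DD versus IP.

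Fourth, development from post-test to transfer is a listed outcome, so a conditional comparison addresses a related question. It does, but that question is not the primary outcome, and a causal reading needs mediation assumptions.

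Finally, section 7.3 allocates teaching by group, so the 5% and 88% reference values, which assume independent participants, are illustrative. The bias formula in step 1 does not rely on that assumption.

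**Conclusion.** The concern holds. For DD versus IP, the post-test is a post-randomisation outcome, its use as a covariate is discretionary, and no far-transfer test is fixed as primary, although the primary outcome itself is named. The bias is −r × shift: zero if the arms truly match at post-test, and 0.15–0.35 SD in magnitude at a 0.5 SD difference for r of 0.3–0.7. The corresponding false-positive rate with no true effect is 5.1–5.8% at a 0.1 SD shift, 5.7–12.4% at 0.3 SD and 7.1–24.8% at 0.5 SD. Discretion alone gives 6.4–8.4% if the significant result is the one reported. These figures rest on assumed correlations and shifts and on independent participants. The point should be corrected before analysis because it affects the primary claim and the trial cannot verify the condition under which adjustment would be harmless.

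**What to change.** In section 8.1, name one primary analysis: the DD versus IP difference in far-transfer OSATS, one score per participant (the mean if both sutures are rated), without the post-test as covariate. On that score the t-test and unadjusted ANOVA are the same test. Remove the post-test as a covariate from the far-transfer and near-transfer between-arm comparisons. Label any post-test-adjusted model exploratory or mediation, and the mixed and repeated-measures models secondary or sensitivity analyses. Adjustment in the near-versus-far comparison need not change.

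In the same edit, reconcile the hypothesis numbering: section 8.1 ties hypothesis 1 to near transfer and hypothesis 2 to the vertical mattress suture, whereas section 5 does the reverse.

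The cost is wording plus a possible loss of precision. Adjustment would cut residual variance by r², that is 9%, 25% or 49% for r = 0.3, 0.5 or 0.7, so at 1.145 SD with no shift the trial accepts 88% power instead of 90%, 95% or 99%. That gain is valid for the total effect only if teaching leaves the post-test unchanged. Section 8.2 takes no credit for a covariate, so 16 per group is unaffected. No pre-teaching skill test is described that could replace the post-test. Accounting for teaching group is a separate matter that this change does not address.

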8.2 The Number of Participants

Learners:

We will recruit n=64 pre-clinical students from the Medical Faculty of Copenhagen University. We are targeting undergraduate students, rather than surgical residents, because we want novice learners, and we believe it is worthwhile to establish efficacy of our intervention group using simpler tasks which can be feasibly studied. We based our sample size on the previous pilot-study which suggests that detecting a large effect on a global rating scale (Hedges g of >0. with an alpha of 0.05 and power of 80% requires at least 13 participants per group with additional participants recruited for potential loss to follow-up²⁴ for a total of 16 per group. Participants will receive a certificate showing completed suturing course, as an honorarium to compensate for their time in the study.

Instructor and Raters:

We will recruit one 2nd year post-graduate surgical trainees to serve as an instructor. We will recruit an instructor who has some experience in teaching or coaching undergraduate students. Additionally, participant performance on the post-

and transfer tasks will be assessed by a blinded rater who will receive video-tapes of all relevant participant performances.

9. Data management

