Study Title:

Using 'Guided-Discovery-Learning' to optimize and maximize transfer of surgical simulation

Internal Short title: GDL-Efficacy
Ethics Ref: H-18041917

NCT: 03684720

Acronym: GDLEFFICACY

Date and Version No: 19.09.2018, vs.0.2

Chief Investigator:

[name], Bach. Med¹

Investigators:

[name] PhD,²

[name],³

[name], MD, Professor¹

[name] MSc. PhD³

[name] PhD,³

Sponsors:

Copenhagen Academy for Medical Education and Simulation, Capital Region, Denmark

Funder:

Application for funding is ongoing.

1. Copenhagen Academy of Medical Education and Simulation, Rigshospitalet; Copenhagen, Denmark.

2. Department of Gynecology and Obstetrics, Hvidovre Hospital, Region H, Zealand, Denmark

3. The Wilson Centre, University Health Network and University of Toronto; Toronto, Ontario

Investigators [name], [name], [name], [name], [name] and [name] have no conflict of interest or financial ties to disclose.

The reporting this study will conform to the CONSORT statement.

Confidentiality Statement

This document contains confidential information that, prior to trial registration at www.clinicaltrials.gov, must not be disclosed to anyone other than the Sponsor, the Investigator Team, host organization, and members of the Research Ethics Committee, unless authorized to do so.

Table of Contents

1. Synopsis	3
2. Abbreviations	3
3. Background and Rationale	3
4. Objective and Outcome Measure.....	6
5. Study Design	6
6. Participant identification	8
7. Study Procedures.....	8
8. Statistics and Analysis	10
9. Data management	11
10. Ethical and Regulatory Consideration.....	11
11. Finance	12
12. Publication Policy	12
13. Appendix A.....	13
14. Appendix B.....	14
15. Appendix C.....	15
16. Appendix D.....	16
17. Appendix E.....	17
18. Appendix F	18
19. Appendix G.....	19
20. References.....	20

1. Synopsis

Study Title	Using 'Guided-Discovery-Learning' to optimize and maximize transfer of surgical simulation
Research Objective	To explore the effect of guided-discovery-learning in transfer of surgical skills
Study Design	A prospective randomized study and explorative study
Study Participants	Students from the Medical Faculty who have not received suture-training
Planned Sample Size	Sixty-four participants
Planned Study Period	Twenty-four months
Objectives	To explore the effect of guided-discovery-learning vs traditional instructor lead teaching in the transfer of basic surgical skills.

2. Abbreviations

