6.1 Study Participants

Participants will be students primarily at the Medical Faculty of Copenhagen University who haven't received surgical education yet. Eighty participants will be included split into two groups. Both groups will be taught, filmed and tested at CAMES.

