7.3 Randomization

Randomization

The study is a double randomized study. Participants will be randomized using en-bloc randomization sequence in groups. After enrollment participants will be assigned a group and a date for teaching. And the groups will then be randomized, and assigned a teaching method, which will be revealed on the date of teaching. Each group will then again be randomized to either to a near-transfer or a far-transfer group for the second phase of the study.

Groups range from A through H, making 8 groups in total. All groups assigned an uneven number will be allocated the intervention, whereas groups assigned an even number will be allocated the control. Furthermore, the 4 groups in the control and the intervention will be randomly assigned to a new number. Groups assigned an uneven number will be allocated the near-transfer group, and groups assigned an even number will be allocated the far transfer group.

For the recording and rating of the test each participant will assigned an identification number (A_1, B_1 etc) which will correspond to an identification key-number in the video (eg. 18920, 32, 564). The conversion key will be stored by the principle investigator and only he will have access to it, thus allowing the raters to score the participants blinded.

All randomization will be done using www.random.org and disclosed by an external party.

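### Section 6.1 enrols eighty participants, but the rest of the plan says 64 and only 64 fits eight groups of 8; the basis for 13 per group in 8.2 also needs confirming

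*Combined protocol and SAP*

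**What the plan says.** Three places in the combined protocol and SAP put enrolment at 64. The synopsis table has "Sixty-four participants", section 5 describes the study as "including n=64 pre-clinical students from the Medical Faculty of Copenhagen University", and 8.2 has "We will recruit n=64 pre-clinical students from the Medical Faculty of Copenhagen University". Section 6.1 differs: "Eighty participants will be included split into two groups".

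The structure is fixed elsewhere. Section 5: "Each group consists of 8 participants". Section 7.3 letters the groups A to H, eight in all, and gives four to each teaching method: discovery then instruction (DD) or instruction then practice (IP). Transfer tasks follow: "Each group will then again be randomized to either to a near-transfer or a far-transfer group for the second phase of the study". Section 4 makes the DD v IP difference in OSATS score on far transfer the primary outcome.

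On size, 8.2 refers to the pilot and to a large effect: "Hedges g of >0. with an alpha of 0.05 and power of 80% requires at least 13 participants per group". It then raises the number to 16 per group for loss to follow-up. The digits after the decimal point and the closing bracket are not readable in the available text. For the between-group differences, 8.1 says "students t-test will be used" and does not give the sides. Its Analysis part also plans an ANOVA for the vertical mattress task and allows covariates such as the post-test score.

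**The concern.** The enrolment total is an operative number. It sets when recruitment stops, how many teaching sessions are booked and how many students make up each comparison. With two totals in the current text, a reader cannot tell from section 6.1 whether 64 enrolled students would mean a completed trial or a shortfall of 16.

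The word *group* adds to the difficulty. It means a teaching session of 8 in section 5, one of two halves of the sample in 6.1, and apparently a cell of 16 in 8.2. The primary comparison is between two such cells, not between two halves of the whole sample, and 8.2 does not say so.

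The secondary matter is that 8.2 is the only readable justification for the size of the far-transfer comparison. A null result there can be interpreted only if the detectable effect is known. Under the simplest reading of the test in 8.1, 13 per arm does not correspond to any effect size that begins with a zero before the decimal point.

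**Working it through.** **Enrolment**

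Inputs: eight groups (7.3), 8 per group (section 5), two teaching methods and two transfer tasks (7.3), 16 per group (8.2).

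- Total: 8 × 8 = 64. This reproduces the synopsis, section 5 and 8.2.
- Cells: 2 methods × 2 tasks = 4; 64 / 4 = 16. This reproduces the 16 in 8.2, so *group* there must be a cell.
- Each far-transfer arm is 16 / 8 = 2 teaching groups.
- For eighty: 80 / 8 groups = 10 per group, against the 8 in section 5; or 80 / 8 per group = 10 groups, against A to H in 7.3. Neither fits.
- Surplus: 80 − 64 = 16.
- Loss allowance already inside 64: (16 − 13) / 16 = 18.75%.

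**Size of the far-transfer comparison**

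Inputs from 8.2: alpha 0.05, power 80%, 13 evaluable or 16 recruited per cell. The plan's own 13 cannot be reproduced, because the effect size is unreadable. The check therefore runs the other way: which effect gives 80% power with 13?

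Method: two-sample t-test, n per arm, df = 2n − 2, noncentrality d × √(n/2), solved for 80% power. Hedges g = d × J, with J = 1 − 3/(4·df − 1).

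| Test | n per arm | d | J | g |
|---|---|---|---|---|
| Two-sided, unadjusted | 13 | 1.145 | 1 − 3/95 = 0.968 | 1.109 |
| Two-sided, unadjusted | 16 | 1.024 | 1 − 3/119 = 0.975 | 0.998 |
| One-sided, unadjusted | 13 | 1.004 | 0.968 | 0.972 |

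The normal approximation for the first row is (1.960 + 0.842) × √(2/13) = 1.10, which is close.

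In the other direction, the two-sided unadjusted test needs 18 per arm at an assumed d of 0.99 (17 if 0.99 is read as g), 21 at 0.9 and 26 at 0.8. With 13 per arm its power is 68%, 60% and 50% at d of 0.99, 0.9 and 0.8. No value below 1 leads to 13.

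Other routes do lead to 13:

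- One-sided test: an assumed g of 0.99 needs exactly 13 per arm.
- Two-sided with one covariate at an assumed correlation of 0.5 (df = 23): 1.148 × √(1 − 0.25) = 0.99.
- A pilot effect of g about 1.11 or more, two-sided and unadjusted.

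All of these ignore allocation by whole groups. The plan gives no intraclass correlation. As an illustration, with 13 / 2 = 6.5 evaluable per group, d is multiplied by √(1 + 5.5 × ICC). Assumed ICCs of 0.02, 0.05 and 0.10 turn 1.145 into about 1.21, 1.29 and 1.43, before any loss of degrees of freedom.

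**The case against.** On enrolment, the best defence is that eighty is an intake target with room for losses, since 64 / 80 = 80% retention. The text does not support this. Section 8.2 says 64 are to be recruited, and it has already placed its loss allowance between 13 and 16 per cell. What does stand is that three of four statements agree and the structure confirms them, so most readers would settle on 64. A reader might infer from 6.1 that 20 per cell were intended, with a detectable d of about 0.91 under the simple two-sided t-test. But 6.1 gives no cell structure, so that figure is extrapolation.

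On power, the opposing case largely succeeds. A reader might infer that the calculation in 8.2 is wrong, that the trial is underpowered for its stated effect, or that 13 was merely carried over from the pilot, which also had 13 per arm. The documents show none of these. The unreadable digits come from how the text was read and may have been accompanied by a qualifier. Sidedness is not stated, and the far-transfer hypothesis in section 3 is directional. Section 8.1 allows covariates. The size is said to rest on the pilot, whose transfer result section 3 describes as strongly in favour of DD, so a pilot g above 1.11 is possible and would satisfy a lower bound beginning with zero.

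It is also fair to object that 1.15 is not a ceiling, because two teaching groups per arm may bring correlation within groups.

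**Conclusion.** The enrolment contradiction stands without any assumption: 6.1 exceeds the total in the synopsis, section 5 and 8.2 by 16, and it cannot be reconciled with eight groups of 8. It should be fixed. Nothing in the readable text suggests that the design itself is affected.

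The power point stands only as a conditional query. If the test is two-sided and unadjusted, and whole-group allocation is ignored, 80% power needs d about 1.15 (g about 1.11) with 13 per arm, or about 1.02 (g about 1.00) with all 16. An effect size below 1 would then not give 13. If any of those conditions fails, 13 may be right. The arithmetic does not establish an error in 8.2.

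**What to change.** 1. Correct 6.1 to 64 participants in eight groups of 8, and check that the flow chart in Appendix B, which is not shown in the available text, agrees.
2. State in 8.2 that a group of 16 is one teaching-method-by-transfer-task cell, so the primary comparison is 16 v 16 recruited and 13 v 13 after the allowed loss.
3. Confirm in 8.2 the full effect size behind 13, whether it is the pilot estimate or a bound, the sidedness, and any covariate assumption. If the test was two-sided and unadjusted with a value below 1, restate the detectable effect as about 1.15 with 13 per arm (1.02 with 16), noting that this makes no allowance for allocation by whole groups.

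The cost is wording: no added enrolment and no change of analysis. The third item may leave a less favourable detectable effect on record. If the sponsor did intend eighty, this is no longer only wording: 16 more students would be needed, and sections 5, 7.3 and 8.2 and the synopsis would have to change.
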